7.2 Safety Analysis Set

The safety analysis set will include all subjects who received at least 1 dose of talimogene laherparepvec. The safety analysis set will be used for efficacy endpoints with the exception that only the first 18 subjects will be used to test the DRR null hypothesis for Dose 1.

7.3 qPCR Analysis Set

The qPCR Analysis Set includes subjects in the Safety Analysis Set with a swab sample obtained for qPCR testing of talimogene laherparepvec DNA from any lesion suspected to be of herpetic origin.

7.4 Subgroup Analyses

See [Section 4.2](#).

8. Interim Analysis and Early Stopping Guidelines

8.1 Interim Analysis

No formal interim efficacy analysis is planned for this study. Interim safety analyses will be performed to support the evaluation of safety by the DLRT (see protocol section 10.3.2).

8.2 Primary Analysis

The primary analysis for safety will occur 3 months after the last subject is enrolled. The primary analysis for efficacy will occur when a durable response outcome has been assessed for all subjects included in the primary efficacy analysis. Safety will be re-analyzed at the primary efficacy analysis.

8.3 Final Analysis

The final analysis will occur 24 months after the last subject is enrolled.

If there are subjects who receive therapy beyond 24 months, a post final analysis of these subjects will occur after the last subject completes safety follow-up.

Adverse events and tumor assessments evaluated after final analysis will be listed for these subjects.

9. Data Screening and Acceptance

9.1 General Principles

The objective of the data screening is to assess the quantity, quality, and statistical characteristics of the data relative to the requirements of the planned analyses.

9.2 Data Handling and Electronic Transfer of Data

The Amgen Global Study Operations-Data Management (GSO-DM) department will provide all data to be used in the planned analyses. This study will use the RAVE database.

9.3 Handling of Missing and Incomplete Data

Every effort will be made to obtain complete data in the clinical study. Partial or missing dates of adverse events, disease-related events, and concomitant medications and incomplete death dates will be imputed. Details of the imputation algorithm are provided in [Appendix A, Section 12](#). Adverse events with missing IP relatedness, seriousness, or CTCAE severity grades will be included in all analyses of TEAEs as long as the events qualify for the reporting period. Events with missing relatedness, seriousness, and severity grades will be excluded from corresponding analyses of TEAEs that are treatment-related, serious, and had a specific CTCAE grade.

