10.5 Handling of Missing and Incomplete Data

Partial or missing dates of adverse events and concomitant medications will be imputed. Adverse events with missing severity and/or possible relationship to talimogene laherparepvec will be included in the all adverse events analyses, except by severity grade and treatment-related. Every effort will be made to obtain complete dates for deaths. Details of the imputation algorithms will be specified in the study-specific statistical analysis plan.

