3.2 Sample Size

Approximately 18 subjects will be enrolled. See protocol Section 10.2. The total number of subjects that will participate in the study and be used in the DLT analysis is approximately 18. The first 6 DLT-evaluable subjects will be used for the decision of dose de-escalation. If there is no dose de-escalation, the first 18 subjects in the safety analysis set will be used for the efficacy analysis of DRR, and the whole safety analysis set will be used for other efficacy analyses including ORR, TTR, DOR, PFS and OS. If dose de-escalation occurs, the efficacy analysis will be performed using the safety analysis set at Dose -1. In the current study design, a dose level will be considered safe if there are 0 to 1 DLTs observed in the initial 6 DLT evaluable subjects.

[Table 1](#) and [Figure 1](#) presents the probability of declaring a dose level safe (unsafe) for a range of true DLT rates for the protocol therapy for the 6 DLT-evaluable subjects (see triangle symbols). As shown below in [Table 1](#), the probability of declaring a dose level safe (unsafe) in the current study (based on only 6 DLT evaluable subjects) is 89% (11%), 42% (58%), and 11% (89%) if the true DLT rate is 10%, 30%, or 50%, respectively. Hypothetically, if the study were to enroll an additional 6 DLT-evaluable subjects after the initial 6 subjects (total of 12 DLT evaluable subjects), the probability of observing a DLT rate \geq 33% in the 12 subjects following the observation of 0-1 DLTs in the first 6 DLT evaluable subjects would be 0.6%, 8.6%, and 6.7% if the true DLT rate is 10%, 30%, or 50%, respectively.

Figure 1. Probability of Declaring a Cohort Safe (Unsafe)

DLT= dose-limiting toxicity; Pr = probability

Table 1. Probability of Declaring a Cohort Safe or Unsafe

| True Cohort DLT Probability | Probability Declare Cohort Safe | Probability Declare Cohort Unsafe |
|-----------------------------|---------------------------------|-----------------------------------|
| 10% | 89% | 11% |
| 20% | 66% | 34% |
| 30% | 42% | 58% |
| 40% | 23% | 77% |
| 50% | 11% | 89% |

DLT= Dose Limiting Toxicity

The total number of subjects that will participate in the study and be used in DLT analyses is approximately 18.

As shown in [Table 2](#), without dose de-escalation, 18 subjects provides maximum power to test the DRR null hypothesis in the range of 16 to 20 subjects, therefore only the first 18 subjects in the safety analysis set will be used in the analysis.

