4.1.3 Safety Endpoints

Subject incidence of all the following, where not defined as DLT:

- adverse events
- grade \geq 3 adverse events
- serious adverse events
- clinically significant laboratory changes
- changes in vital signs

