10.6 Safety Analyses

10.6.1 DLT Analysis

The subject incidence of DLT based on CRF will be summarized as a binary variable using the DLT Analysis Set by calculating the frequency, percentage, and exact 95% CI.

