10.6.2 Adverse Events

The Medical Dictionary for Regulatory Activities (MedDRA) version 18.0 or later will be used to code all adverse events (AE) to a system organ class and a preferred term. The CTCAE version 4.0 will be used to grade severity of adverse events. In general, events with missing IP relatedness, seriousness, or CTCAE severity grades are included in the analysis of treatment emergent AE as long as the event meets the criteria for a TEAE. However, analyses of treatment-related, SAE, or grade 3 or higher, or combination thereof will exclude events with missing relatedness, seriousness, and severity grades, respectively.

The analyses for AEs will include TEAEs (ie, occurring in the treatment period) unless otherwise specified. The subject incidence of TEAEs will be summarized for all AEs, serious AEs, AEs leading to withdrawal of investigational product, worst grade 3 or 4 AEs, and fatal AEs. The subject incidence of all treatment-related AEs, serious AEs, AEs leading to withdrawal of investigational product, worst grade 3 or 4 AEs, and fatal AEs will be tabulated by system organ class (SOC) and preferred term in descending order of frequency.

A listing of fatal AEs will be provided. A listing of all SAEs reported in the clinical database with an event onset from consent will be provided with onset reported relative to the first and most recent dose of study therapy and identification as a TEAE.

Subject incidence of DREs (disease-related events) and fatal disease related events will be tabulated by system organ class and preferred term. Selected safety analyses may also be performed in which DREs are considered to be a TEAE.

Treatment-related AEs reported in long term follow-up will be summarized in this study at the final analysis and also separately at a program-level.

Potential or known unintended exposure to talimogene laherparepvec, related suspected herpetic signs or symptoms, and detection of talimogene laherparepvec in a subject's household member, caregiver, or healthcare provider will be reported to Amgen.

Exposures, signs or symptoms will be summarized and also analyzed separately at a program-level.

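### Adverse events with a missing relatedness, seriousness or grade drop out of the matching safety tables, and no planned output shows how many; any effect can only lower those incidences

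*SAP*

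**What the plan says.** SAP 9.3 sets two rules for an adverse event whose relatedness, seriousness or CTCAE grade is missing. First, such events "will be included in all analyses of TEAEs as long as the events qualify for the reporting period". Second, they leave the tables defined by the missing attribute: "Events with missing relatedness, seriousness, and severity grades will be excluded from corresponding analyses of TEAEs". SAP 10.6.2 restates the second rule and names the tables: "analyses of treatment-related, SAE, or grade 3 or higher, or combination thereof will exclude events with missing relatedness, seriousness, and severity grades, respectively".

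Protocol 10.5 has the same rule for severity and relatedness: such events "will be included in the all adverse events analyses, except by severity grade and treatment-related". It does not mention seriousness, so that exclusion appears only in the SAP.

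The affected tables matter to the trial. SAP 4.1.3 defines the safety endpoints as "Subject incidence of all the following, where not defined as DLT", and the list includes grade 3 or higher adverse events and serious adverse events. SAP 10.6.2 plans the treatment-related tables. The primary safety endpoint is handled separately in SAP 10.6.1: "The subject incidence of DLT based on CRF will be summarized as a binary variable using the DLT Analysis Set".

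Neither document plans a worst-case analysis, a missing category, or a count or listing of the events removed.

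**The concern.** Leaving an event out of a table has the same numerical effect as classing it as unrelated, non-serious or below grade 3. The rule therefore works in one direction: it can lower an incidence or leave it unchanged, but cannot raise it. For a safety summary that is the non-conservative default.

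SAP 9.3 imputes partial or missing adverse event dates, so the plan already accepts imputation for incomplete event records. For the attributes that define the serious, related and severe tables it excludes instead, and a reader of the report could not tell whether the rule was applied never or several times. With about 18 subjects, one reclassified subject visibly moves an incidence and its confidence limit.

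**Working it through.** **Inputs**
- Denominator: 18, from SAP 3.2 ("Approximately 18 subjects will be enrolled").
- Rule: an event is removed only from the table that matches its missing attribute (SAP 9.3, 10.6.2).
- Missing rate: not in the documents, so it is an assumption and is shown over a range.

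The plan attaches no figure to this rule, so there is nothing to reproduce.

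**Step 1: effect of one subject.** A subject drops out of a subject-level incidence only if every event that would qualify that subject lacks the attribute. The loss is then 1/18 = 5.6 percentage points.

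**Step 2: effect on the interval.** These are Clopper-Pearson 95% limits, the exact method the SAP names for binomial proportions in 10.5. For zero events the upper limit is 1 − 0.025^(1/18) = 18.5%. For x events it is the 97.5th percentile of a Beta(x + 1, 18 − x) distribution.

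| Subjects | Incidence | 95% CI |
|---|---|---|
| 0/18 | 0% | 0 to 18.5% |
| 1/18 | 5.6% | 0.1 to 27.3% |
| 2/18 | 11.1% | 1.4 to 34.7% |
| 3/18 | 16.7% | 3.6 to 41.4% |

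Losing one subject moves the result up one row of this table: 1/18 is reported as 0/18, or 3/18 as 2/18.

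**Step 3: how likely that is.** As an illustration, let p be the true subject incidence, m the number of qualifying events per affected subject, and q the chance that an event's attribute is missing, independently across events. A subject is lost with probability p·q^m. So:
- expected bias = −p·q^m
- chance that at least one of 18 subjects is lost = 1 − (1 − p·q^m)^18

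With one qualifying event per affected subject (m = 1), each cell gives the expected bias in points and the chance of losing at least one subject:

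| p | q = 1% | q = 5% | q = 10% |
|---|---|---|---|
| 10% | −0.1; 1.8% | −0.5; 8.6% | −1.0; 16.5% |
| 20% | −0.2; 3.5% | −1.0; 16.5% | −2.0; 30.5% |
| 30% | −0.3; 5.3% | −1.5; 23.8% | −3.0; 42.2% |

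For example, p = 20% and q = 5% give p·q = 0.01, and 1 − 0.99^18 = 16.5%.

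With two qualifying events (m = 2) at p = 20%, the bias is −0.002, −0.05 and −0.2 points, and the chance is 0.04%, 0.9% and 3.5%. With q = 0 both are zero.

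**The case against.** The strongest reply is that the rule will rarely apply. Protocol 9.2.2.1 requires the investigator to assign severity and relatedness to every adverse event, with relatedness a yes-or-no answer. Protocol 12.3 has data checked for omissions and queried. Serious events also go through 24-hour reporting with follow-up (Protocol 9.2.2.2), and SAP 10.6.2 lists all reported serious and fatal events. The rule is pre-specified and agrees with Protocol 10.5 where the two overlap. Safety carries no formal hypothesis test (SAP section 5).

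Most of this stands and keeps the point small. Some gaps remain. Seriousness is not among the attributes listed in Protocol 9.2.2.1. A listing of serious events may not show one whose seriousness is blank. None of the planned outputs identifies the excluded events.

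It is also fair that 0/18 against 1/18 is the starkest example. It is unlikely for the table of all treatment-related events: Protocol 2.2 reports at least one adverse event in 99.3% of treated phase 3 subjects, and several adverse drug reactions at 25% or more. It is more relevant to the sparser tables, such as serious or severe events.

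A reader might infer that missing attributes cluster late in follow-up or near death. The documents do not support this. After the safety follow-up visit, non-serious events are collected only if related (Protocol 9.2.2.1), so relatedness is already judged. A fatal outcome is itself a seriousness criterion (Protocol 9.1.3), and death is equated with grade 5 in Protocol 6.2.1.2.2.

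Finally, counting missing as positive is also one-directional. That is a reason to show both figures side by side and not to replace one with the other.

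**Conclusion.** The point holds in conditional form and is minor. The rule can bias the treatment-related, serious and grade 3 or higher incidences downward, by 5.6 points of 18 for each subject with no other qualifying event. The bias is zero if no attribute is missing at analysis. Its actual size cannot be established, because the documents give no missing rate; the ranges above rest on assumed rates of 1% to 10% and independence between events.

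A reader might go further and infer that the plan biases its key safety results downward. The documents do not support that. All-TEAE incidence keeps these events. DLT incidence is summarised from the CRF in its own analysis set and is not among the tables the rule names, even though a DLT itself needs a relatedness judgement (Protocol 6.2.1.2.2). What remains is a non-conservative rule whose use would go unseen in the report.

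**What to change.** Amend SAP 9.3 and 10.6.2 only. Keep the analysis that Protocol 10.5 describes, and add:
- a missing row in the treatment-related, serious and grade 3 or higher tables;
- a worst-case line in each table, counting TEAEs with missing relatedness as treatment-related, and those with missing seriousness or grade as serious or as grade 3 or higher;
- a listing of the TEAEs with any of these attributes missing.

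The two lines then bracket the incidence. If nothing is missing they coincide and the report can say so.

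The cost is a few sentences of SAP text and minor programming. The downside is a slightly higher incidence on the worst-case line if any values are missing. Because the Protocol 10.5 analysis stays and the new figures sit beside it, no protocol amendment is needed, and so none of the investigator agreement and ethics approval that Protocol 12.1 attaches to one.

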9.4 Detection of Bias

Lack of protocol compliance may introduce potential bias in the estimation of protocol endpoints. All important protocol deviations (IPDs) will be reported, documented and stored in eClinical (a clinical trial management system). IPD reports will be produced using Cognos by the study manager and will be regularly reviewed in the study team's IPD review meetings as well as before analysis.

Protocol compliance will be examined by tabulating subjects with IPDs.

9.5 Outliers

Descriptive statistics will be used to identify outliers in any key variables. Suspected outliers will be included in all analyses unless there is sufficient scientific justification to exclude them.

9.6 Distributional Characteristics

All binary endpoints will be assumed to follow a binomial distribution. The Kaplan-Meier estimates for the probability of time-to-event endpoints are non-parametric.

9.7 Validation of Statistical Analyses

Programs will be developed and maintained, and output will be verified in accordance with current risk-based quality control procedures.

Tables, figures, and listings will be produced with validated standard macro programs where standard macros can produce the specified outputs.

The production environment for statistical analyses consists of Amgen-supported versions of statistical analysis software; for example, the SAS System version 9.2 or later.

10. Statistical Methods of Analysis

10.1 General Principles

The DLT Analysis Set will be used to summarize the subject incidence of DLT and the Safety Analysis Set will be used for all other analyses of safety and efficacy endpoints.

Descriptive statistics will be provided for efficacy and safety endpoints for all subjects. Summary statistics including mean, standard deviation, median, first and third quartiles, minimum and maximum will be provided for continuous variables. Frequency and percentage will be summarized for binary and categorical variables. Proportions and the corresponding exact 95% confidence intervals using F distributions will be calculated. Exact tests will be considered for subgroup analyses. Time to-event endpoints will be estimated using the K-M method per [Kalbfleisch and Prentice \(1980\)](#) and confidence intervals for quartiles will be estimated per [Brookmeyer & Crowley \(1982\)](#).

Separate reporting at a program-level may occur of close contact and HCP events with or without a known unintended exposure.

10.2 Subject Accountability

The number of subjects enrolled will be tabulated by investigator sites. Subject disposition (including the number screened, enrolled, treated, ended treatment, that completed the safety follow-up visit, and that completed the study) will be summarized separately for all enrolled subjects. Reasons for not receiving treatment, for ending treatment, not completing the 30-day safety follow-up visit, and ending the study will be provided.

10.3 Important Protocol Deviations

Important Protocol Deviations (IPDs) categories are defined by the study team before the first subject's visit and updated during the IPD reviews throughout the study prior to database lock. These definitions of IPD categories, sub-category codes, and descriptions will be used during the course of the study. Eligibility deviations are defined in the protocol. Eligibility deviations that are defined as IPDs will be summarized in both the IPD and Eligibility Deviation table and IPD and Eligibility Deviation listings.

10.4 Demographic and Baseline Characteristics

Summary statistics of the following demographic and baseline characteristics will be tabulated using the Safety Analysis Set.

- Age at baseline: < 50, ≥ 50; < 65, ≥ 65; < 75, ≥ 75 years
- Sex (female vs male)
- Disease stage at baseline: IIIB and IIIC vs IVM1a vs IVM1b vs IVM1c
- Line of therapy for current disease
- Type of prior therapy
- BRAF status
- Baseline HSV-1 serostatus
- Baseline LDH ≤ ULN vs > ULN
- ECOG (0 vs 1)
- Other covariates reported in the literature or from other Amgen studies maybe considered in the analysis as appropriate and if feasible at the time of analysis.

10.5 Efficacy Analyses

In general, the analysis of efficacy endpoints will be based on the Safety Analysis Set with the exception that only the first 18 subjects will be used to test the DRR null hypothesis for Dose 1.

- DRR and ORR (CR+PR) will be summarized with associated exact 95% CIs for binomial proportions (Clopper & Pearson 1934). A 1-sided 5% significance level exact binomial test will be performed for a DRR > 2%. If there are more than 18 subjects in the safety set for Dose Level 1, the test will be based on the first 18 enrolled subjects; otherwise, it will be based on all subjects in the safety set for either Level 1 or -1). If there is no dose de-escalation, the DRR/ORR for Dose 1 will be estimated using both the first 18 subjects and all treated.
- DRR/ORR will be summarized by planned covariates (grouped disease stage and lines of therapy) as in Section 4.2.
- DOR among responders, PFS and OS will be estimated using the Kaplan-Meier method and estimates of event time quartiles, event-free rates at selected times and the corresponding 95% CIs will be provided.
- Summary statistics will be estimated for TTR among responders.

10.6 Safety Analyses

10.6.1 DLT Analysis

The subject incidence of DLT based on CRF will be summarized as a binary variable using the DLT Analysis Set by calculating the frequency, percentage, and exact 95% CI.

10.6.2 Adverse Events

The Medical Dictionary for Regulatory Activities (MedDRA) version 18.0 or later will be used to code all adverse events (AE) to a system organ class and a preferred term. The CTCAE version 4.0 will be used to grade severity of adverse events. In general, events with missing IP relatedness, seriousness, or CTCAE severity grades are included in the analysis of treatment emergent AE as long as the event meets the criteria for a TEAE. However, analyses of treatment-related, SAE, or grade 3 or higher, or combination thereof will exclude events with missing relatedness, seriousness, and severity grades, respectively.

The analyses for AEs will include TEAEs (ie, occurring in the treatment period) unless otherwise specified. The subject incidence of TEAEs will be summarized for all AEs, serious AEs, AEs leading to withdrawal of investigational product, worst grade 3 or 4 AEs, and fatal AEs. The subject incidence of all treatment-related AEs, serious AEs, AEs leading to withdrawal of investigational product, worst grade 3 or 4 AEs, and fatal AEs will be tabulated by system organ class (SOC) and preferred term in descending order of frequency.

A listing of fatal AEs will be provided. A listing of all SAEs reported in the clinical database with an event onset from consent will be provided with onset reported relative to the first and most recent dose of study therapy and identification as a TEAE.

Subject incidence of DREs (disease-related events) and fatal disease related events will be tabulated by system organ class and preferred term. Selected safety analyses may also be performed in which DREs are considered to be a TEAE.

Treatment-related AEs reported in long term follow-up will be summarized in this study at the final analysis and also separately at a program-level.

Potential or known unintended exposure to talimogene laherparepvec, related suspected herpetic signs or symptoms, and detection of talimogene laherparepvec in a subject's household member, caregiver, or healthcare provider will be reported to Amgen.

Exposures, signs or symptoms will be summarized and also analyzed separately at a program-level.

